
>30 days
 
Patients need at least two days of exposure to the index NOAC to ensure they had at least one day of index NOAC exposure in the post-index follow-up period. A sensitivity analysis will also be performed using a 14 day treatment gap.
 
Both claims-level data, including diagnosis codes, procedure codes, pharmacy dispensed drugs, cost information, and enrolment data, as well as EHR-level data, including relevant lab tests and results, will be extracted for all applicable patients. Patient demographics, treatment history, and comorbidities, will be derived from the electronic database. Start and stop dates of each course of treatment will be coded from the pharmacy and medical claims data using rules to be developed in the study protocol. Comorbidities of interest will be ascertained through ICD-9 and ICD-10 diagnosis codes, in combination with procedures and medications, as appropriate to the study protocol definitions.
 
To account for potential selection bias, the study cohorts (dabigatran/rivaroxaban and dabigatran/apixaban) will be matched on their baseline characteristics using the propensity score matching (PSM) method. The PSM aims to balance the two treatment groups on baseline demographics, health plan type and clinical characteristics. The feasibility of PSM will be evaluated based on available sample size and descriptive results. If patient characteristics between dabigatran/rivaroxaban and dabigatran/apixaban cohorts are significantly different, i.e., less than 50% of patients in the dabigatran group can be matched to the rivaroxaban or apixaban group based on PSM, then the study design will be re-evaluated before proceeding to analysis. The Nearest Neighbor method of propensity score matching within a caliper of 0.10-0.20 (depending on resulting sample sizes) of the standard deviation of the estimated logit will be used to select the matched samples.
 
The propensity score models will include baseline variables known to be confounders or factors related to the outcome only, including age, gender, health plan type, geographic region, month and year of index date, Charlson comorbidity index (CCI), stroke risk scores (i.e. CHADS₂ or CHA₂DS₂-VASc), bleeding risk scores (i.e., modified HAS-BLED), specified comorbid conditions and medication use, based on literature and clinical relevance, as well as empirical data (top diagnoses, procedures, etc.) that may account for possible unforeseen confounding.

--

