The propensity score will be defined as the probability of being treated with the index NOAC based on a set of baseline characteristics. If, for example, two patients, one in the dabigatran group and another in the rivaroxaban group, had the same propensity score, they would both have the same probability of being treated with dabigatran. The final list of baseline characteristics to be utilized in the PSM will be decided in conjunction with BI. The following baseline characteristics in the pre-index period will be considered: age, gender, health plan type, geographic region, month and year of index date, Charlson comorbidity index (CCI), stroke risk scores (i.e. CHADS₂ or CHA₂DS₂-VASc), bleeding risk scores (i.e., modified HAS-BLED), relevant baseline comorbid conditions and medication use as defined in Section 9.3.3. The distribution of baseline characteristics will be presented before and after the matching process. For baseline covariates that are not sufficiently balanced after PSM, the covariates will be included in an appropriate multivariate model to adjust for those differences.

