ANNEX 1. LIST OF STAND-ALONE DOCUMENTS

APPENDIX A. VARIABLE CODING LIST**Table 1. NOACs for Exposure**

Class	Description	GPI Code
Direct thrombin inhibitors	Dabigatran	833370302001
Direct Xa inhibitor	Rivaroxaban Apixaban	83370060 83370010

Table 2. Baseline Comorbid Conditions

Comorbidity		
Cancer	140.xx-172.xx, 174.xx-208.xx, 230.xx-231.xx, 233.xx-234.xx	C00.xxx-D49.xxx
Rheumatoid arthritis	714.xx	M05.xxx, M06.xxx, M08.xxx, M12.0xx
Multiple sclerosis	340	G35
Coronary artery disease	411.xx, 412.xx, 413.xx, 414.xx, 429.2	I20.x, I24.x, I25.xxx
Acute myocardial infarction	410.xx	I21.xx
Cardiomyopathy	425.xx	I42.x, I43
Ischemic stroke	433.x1, 434.x1, 436.x	I63.xxx, I67.89
TIA	435.x	G45.0, G45.1, G45.2, G45.8, G45.9, G46.0, G46.1, G46.2
Heart failure	402.x1, 404.x1, 404.x3, 428.xx	I11.0, I13.0, I13.2, I50.1, I50.2x, I50.3x, I50.4x, I50.9
Atrial flutter	427.32	I48.92
Hypertension	401.x, 402.x0, 403.xx, 404.x0, 404.x2, 405.xx	I10, I11.9, I12.x, I13.1x, I15.x, I16.x
Peripheral artery disease	440.xx, 443.xx	I70.xxx, I73.xx, I77.7x, I79.1, I79.8
Liver disease	121.1, 423.2, 570-573.xx, 751.62	B661, I311. K70.0-K77, Q446
Renal disease	580.xx-588.xx,	N0x.x, N08, B52.0, E08.2x, E09.2x, N14.x, N15.x, N17.x, N18.x, N19, N25.0, N25.1, N25.9, N25.81, N25.89, N26.x,
	590.xx-593.xx	N10, N11.x, N12, N13.0, N13.0, N13.1, N13.2, N13.30, N13.39, N13.4, N13.5, N13.6, N13.70, N13.71, N13.732, N13.729, N13.721, N13.731, N13.722, N13.739, N13.8, N13.9, N15.x, N16, N20.x, N22, N28.1, N28.0, N28.81, N28.83, N28.84, N28.85, N28.86, N28.89, N28.9, N29, R80.2
COPD/emphysema	490-492.xx, 496	J40.x-J44.x

Hypothyroidism	243-244.x	E00.x, E01.8, E02, E03.0, E03.1, E03.2, E03.3, E03.4, E03.8, E03.9, E89.0
Diabetes	250.xx	E10.xxxx, E11.xxxx, E13.xxxx
Peptic ulcer/GERD	530.11, 530.81, 536.2, 536.8, 787.1, 533.xx	K21.x, K27.x, K30, R11.10, R12
Venous thromboembolism	415.11, 415.19, 451.1x, 451.2, 451.81, 451.83, 451.84, 451.9, 453.4x, 453.8x, 453.9	I2699, I80.1x-I80.9, I82.4xx, I82.6xx, I82.890, I82.90, I82.A1x, I82.B1x, I82.C1x
Hyperlipidemia	272.0 – 272.4	E78.0x-E78.5
HIV infection	V08, 042, 079.53	Z21, B20, B97.35
Bone Marrow disease		
Thrombocytopenia	287.3, 287.4, 287.5	D69.3, D69.4x, D69.5x, D69.6
Chronic anemia	285.2	D63.x
Myelofibrosis	289.83	D75.81
Coagulopathy	286.0-286.9, 287.1, 287.3-287.5	D65-D68.x, D69.1, D69.3-D69.6
Dyspepsia	536.8	K30
Left ventricular heart failure	428.1	I50.1
Bone marrow disease	289.9	D75.9
Thrombocytopenia	287.5	D69.6
Anemia	285.9	D64.9

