Mild Liver Disease	571.2x, 571.4x, 571.5x, 571.6x	K70.2, K70.3x, K73.x, K74.xx, K75.4
Diabetes (mild to moderate)	250.0x, 250.1x, 250.2x, 250.3x, 250.7x	E10.1x, E10.5x, E10.641, E11.0x, E11.5x, E11.641, E13.0x, E13.1x, E13.5x, E13.641, E13.9
Diabetes with Complications	250.4x, 250.5x, 250.6x	E10.3xxx, E10.4x, E10.610, E11.2x, E11.3xxx, E11.4x, E11.610, E13.2x, E13.3xxx, E13.4x, E13.610
Hemiplegia or Paraplegia	342.x, 344.1x	G81.xx, G82.2x
Renal Disease	582.x, 585.x, 586.x, 588.x	N03.x, N18.x, N19, N25.xx, N27.x
Malignancy	140.x-172.x, 174.x-195.x, 201.x, 203.x, 205.x-208.x	C00.x-C43.xx, C45.x-C49.xx, C50.xxx-C76.xx, C81.xx, C88.2, C88.3, C88.8, C88.9, C90.xx, C92.xx-C95.xx, D03.xx, D45
Moderate or Severe Liver Disease	572.2x-582.8x, 456.0x, 456.1x, 456.2x	I85.xx, K72.1x, K72.9x, K75.0, K75.1, K75.2, K75.3, K75.8x, K75.9, K76.1, K76.3-K76.9, K77, K80.xx-K90.49, K90.89, K90.9, K91.2, K91.5, K92.0, K92.1, K92.2, N00.0-N03.8, N04.0-N04.9
Metastatic Solid Tumor	196.x-199.x	C77.x-C79.x, C80.x
AIDS	042.x-044.x	B20
Chronic Obstructive Pulmonary Disease and allied conditions	490.x	J40
	491.x	J41.1, J41.8, J44.x, J42
	492.x	J43.x
	493.x	J45.xxx, J44.x
	494.x	J47.x

	495.x	J67.x
	496.x	J44.9

2. If a patient had both the milder and more severe form of the condition, only count the more severe form of the condition -- Diabetes (mild to moderate) / Diabetes with complications; Mild liver disease / Moderate or severe liver disease; Malignancy / Metastatic solid tumor.
3. Weight each of the baseline conditions by the given weights and sum the number of conditions the patient has at baseline. This sum is the patient's CCI at baseline.

Table 5. CHADS₂ Stroke Risk Score

CHADS ₂ Risk Criteria		
Congestive Heart Failure	428.x	I50.xx
Hypertension	401.x-405.x, 437.2	I10-I16.x, I67.4
Diabetes	250.x	E10.xxxx, E11.xxxx, E13.xxxx
Stroke/ transient ischemic attack (TIA)	433.x1, 434.x1, 435.x, 436, 437.1x, 437.9x, 438.x	G45.0-G45.2, G45.8-G46.2, I63.xxx, I67.8xx, I67.9, I69.xxx

After assessing the risk factors and adding up the risk score, the stroke risk classifications are as below:

Score	CHADS ₂ Stroke Risk Classification
0	Low
1	Intermediate
2-6	High

Table 6. CHA₂DS₂-VASc Stroke Risk Score

CHA ₂ DS ₂ -VASc Criteria		
Congestive heart	428.x,	I50.xx,

failure or left ventricle dysfunction	398.91, 402.01, 402.11, 402.91, 404.01, 404.11, 404.91, 404.03, 404.13, 404.93, 425.4, 425.5, 425.7	I09.81, I11.0, I13.0, I13.2, I42.5, I42.6, I42.8, I42.9, I43

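### The ICD-10 side of the Table 2 cancer covariate is one unbroken range, broader than its ICD-9 side, so the flag widens wherever ICD-10 codes enter the baseline

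*Combined protocol and SAP*

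**What the plan says.** In Annex 1, Appendix A, Table 2, the ICD-9 entry for cancer is "140.xx-172.xx, 174.xx-208.xx, 230.xx-231.xx, 233.xx-234.xx" and the ICD-10 entry is "C00.xxx-D49.xxx". The column headings are missing from the text as supplied, but Section 9.3.3 points to Table 2 for both ICD-9-CM and ICD-10 codes.

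Table 4 of the same appendix has a Charlson malignancy row. Its ICD-9 entry is "140.x-172.x, 174.x-195.x, 201.x, 203.x, 205.x-208.x". Its ICD-10 entry begins "C00.x-C43.xx, C45.x-C49.xx, C50.xxx-C76.xx" and ends "C92.xx-C95.xx, D03.xx, D45".

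Both coding systems feed the covariates. The Abstract says: "Comorbidities of interest will be ascertained through ICD-9 and ICD-10 diagnosis codes". Cancer is listed in Section 9.3.3 and again among the reported baseline conditions in Section 9.7.1. Section 9.7 names "relevant baseline comorbid conditions and medication use as defined in Section 9.3.3" as candidates for the propensity score, together with the Charlson index, the stroke and bleeding scores and "month and year of index date". The final list is to be agreed with the sponsor.

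**The concern.** The ICD-9 entry steps around single categories (173 and 232) and a long block (209-229), and it stops at 234. That looks like a deliberate choice of what counts as cancer. The ICD-10 entry makes no such choice, and nothing in the documents reconciles the two. A patient whose only qualifying codes fall in a category that the ICD-9 list omits is negative while ICD-9 is in use, but can become positive under ICD-10.

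At stake is a covariate that is a candidate for the propensity score, appears in the balance check and is reported as a baseline characteristic. If its meaning drifts with calendar time, and drug choice also drifts with calendar time, part of any cancer difference between the unmatched groups would be a coding artefact. Matching on the flag would also equate patients who meet different definitions.

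**Working it through.** The plan states no figure that depends on this code list, so there is none to reproduce. The check compares the code lists and then asks how much of each study window they can touch.

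**Step 1. The two sides of the Table 2 row, by three-character position.**
- ICD-9: 33 (140-172) + 35 (174-208) + 2 (230-231) + 2 (233-234) = 72 positions. The row spans 140 to 234, which is 95 positions, so 95 − 72 = 23 are skipped: 173, the 21 positions 209-229, and 232. Everything after 234 is also left out.
- ICD-10: 100 (C00-C99) + 50 (D00-D49) = 150 positions, with none skipped.

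These counts describe the breadth of the definition. Not every position need be a code in use, and the counts say nothing about how many patients would be reclassified.

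**Step 2. The plan's own benchmark.**

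| | Table 2 cancer | Table 4 Charlson malignancy |
|---|---|---|
| ICD-9 173 | omitted | omitted |
| ICD-10 C44 | included | omitted (C43 is followed by C45) |
| ICD-9 230-231, 233-234 | included | omitted |
| ICD-9 200, 202, 204 | included | omitted |
| D00-D49 | all 50 positions | D03 and D45 only (48 omitted) |

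The first two lines are like for like: the same ICD-9 gap is carried over in one table and lost in the other. The D-code line is only suggestive, because the two rows do not start from the same ICD-9 ranges.

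**Step 3. How much of each window is exposed.** Index dates run from 1 July 2011 (rivaroxaban comparison) or 28 December 2012 (apixaban comparison) to 30 June 2016 (Section 9.2). The documents give no switch date, so it is an assumption here. Share = time from switch to 30 June 2016 ÷ length of the window.

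| Assumed switch | Rivaroxaban comparison | Apixaban comparison |
|---|---|---|
| 1 July 2015 | 20.0% | 28.5% |
| 1 October 2015 | 9/60 months = 15% | 9/42 months = 21% |
| 1 January 2016 | 9.9% | 14.1% |

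These are shares of calendar time, not of patients.

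**Step 4. How much of an exposed baseline is ICD-10.** With a switch on 1 October 2015, the latest index date has at most 9 of its 12 baseline months under ICD-10. If index dates are evenly spread over those 9 months (assumption), the mean is 9/2 = 4.5 of 12 months. No patient has a baseline coded wholly in ICD-10.

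**Step 5. Is calendar time tied to drug choice?** The feasibility counts in the Abstract are 16,604 dabigatran starters from July 2011 and 6,050 from 28 December 2012. If the second count is a subset of the first (assumption), 16,604 − 6,050 = 10,554 started in the first 18 of 60 months, and 10,554/16,604 = 64%. Before matching, dabigatran use would then be concentrated in the ICD-9 period.

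**The case against.** The strongest reply is that the plan already limits the damage in three ways.

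- Month and year of index date are listed for the propensity score. The Abstract says the models will include them; Section 9.7 says they will be considered. If they are used, early starters tend to be matched with comparators coded under the same system. This is a real mitigation but a partial one: it does not restore the flag's meaning within the ICD-10 months, and the final list is still open.
- Section 9.3.3 sets the flag only on an inpatient claim or two office or emergency visits. A single outpatient code for a minor lesion does not count. This stands, and it limits reclassification.
- The Charlson index has its own, narrower malignancy rows and is also listed for the propensity score, so malignancy enters by a second route. This stands too, although only as part of a summed score.

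A reader might also infer more than the documents support:

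- That the covariate means one thing for early starters and another for late ones. Under an October 2015 switch it is ICD-9 only for most of the window and a mixture at the end.
- That some stated share of late cancer flags is spurious. The documents give no cancer prevalence under either definition, so any such share would be arithmetic on invented inputs.
- That matched groups will look balanced on cancer while truly differing. That requires calendar imbalance to survive matching, which the documents do not show.
- That the Charlson row is a template for the whole mapping. It is a template for C44 only. Which D codes correspond to the omitted ICD-9 blocks has to be read from a code crosswalk, which the documents do not contain.

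**Conclusion.** The row is wrong as written. The two sides of the cancer definition do not match, the plan's Charlson row shows that the gap at 173 can be carried over, and no section explains the difference. The consequence is minor. Assuming an October 2015 switch, it reaches 15% of the calendar window in the rivaroxaban comparison and 21% in the apixaban comparison, through baselines that are only partly ICD-10. No exposure or outcome definition is touched. The effect on the hazard ratios is likely small and cannot be quantified from the documents. This is a code-list correction worth making because it is cheap, and not a threat to the main comparison.

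**What to change.** In Appendix A, Table 2, replace the single ICD-10 range with the ICD-10 counterparts of each listed ICD-9 block in turn: 140-172, 174-208, 230-231 and 233-234. Leave out C44 and any D code that corresponds to an omitted ICD-9 block. Decide D03 and D45 explicitly and consistently with the Charlson row, which counts both; a rule of C codes plus in-situ counterparts would not settle either one.

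Then tabulate the prevalence of the flag by calendar month of index date, by drug, across the coding switch. A step at the switch would show that the mapping is still uneven. State the switch date used, and keep index month and year in the final propensity model.

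Cost: one cell in a code table and one descriptive check. No new data are needed.

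### Table 2 hypertension and CHADS2 heart failure each leave out the hypertensive heart-failure codes that other Appendix A tables count

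*Combined protocol and SAP*

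**What the plan says.** All code lists are in Annex 1, Appendix A.

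- **Table 2, Hypertension:** "401.x, 402.x0, 403.xx, 404.x0, 404.x2, 405.xx" in ICD-9 and "I10, I11.9, I12.x, I13.1x, I15.x, I16.x" in ICD-10.
- **Table 2, Heart failure:** "402.x1, 404.x1, 404.x3, 428.xx" in ICD-9 and "I11.0, I13.0, I13.2, I50.1, I50.2x, I50.3x, I50.4x, I50.9" in ICD-10.
- **Table 5, CHADS2:** the heart-failure row reads "Congestive Heart Failure 428.x I50.xx". The hypertension row is "401.x-405.x, 437.2" in ICD-9, with I10 to I16.x and I67.4 in ICD-10.
- **Table 6, CHA2DS2-VASc:** the hypertension row is the same as in Table 5. Besides 428.x and I50.xx, the heart item lists "402.01, 402.11, 402.91, 404.01, 404.11, 404.91, 404.03, 404.13, 404.93, 425.4, 425.5, 425.7" in ICD-9 and "I09.81, I11.0, I13.0, I13.2, I42.5, I42.6, I42.8, I42.9, I43" in ICD-10.
- **Table 7, HAS-BLED:** hypertension is 401.x to 405.x / I10 to I16.x, and antihypertensive drugs are also listed.

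Section 9.3.3 sets the capture rule for the Table 2 conditions: one inpatient claim, or two office or emergency visits, in the 12-month baseline. Section 9.7 names the stroke scores, the bleeding score and the individual comorbid conditions as candidates for the propensity score. It also says that baseline characteristics will be shown before and after matching.

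**The concern.** Six codes describe hypertension and heart failure together: 402.x1, 404.x1, 404.x3, I11.0, I13.0 and I13.2. The plan itself treats them as heart failure in Tables 2 and 6 and as hypertension in Tables 5, 6 and 7. Yet Table 2 does not count them as hypertension, and CHADS2 does not count them as heart failure. The documents give no reason for either gap.

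The same claim can therefore give opposite answers in two covariates offered to the same propensity model. Those covariates help decide who is matched, whether the matched groups look balanced, and which variables go into the adjusted outcome model. Section 9.7 also leaves open whether CHADS2 or CHA2DS2-VASc is used. For these patients the two scores differ because CHADS2 leaves out codes that Table 2 itself calls heart failure.

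**Working it through.** The plan states no figure to reproduce. The check is code membership: take one code, see which lists contain it, and add the points.

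**Reading of the lists.** A trailing x is read as any further digits. Appendix A uses it that way: diabetes is 250.xx in Table 2 and 250.x in Table 5. A range such as 401.x-405.x therefore includes 402.91, and I10-I16.x includes I11.0.

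**Membership by code (1 = listed, 0 = not listed).**

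| Code | Table 2 heart failure | Table 2 hypertension | CHADS2 heart failure | CHADS2 hypertension | CHA2DS2-VASc heart item | CHA2DS2-VASc hypertension | HAS-BLED hypertension |
|---|---|---|---|---|---|---|---|
| 402.01, 402.11, 402.91 | 1 | 0 | 0 | 1 | 1 | 1 | 1 |
| 404.01, 404.03, 404.13 | 1 | 0 | 0 | 1 | 1 | 1 | 1 |
| I11.0, I13.0, I13.2 | 1 | 0 | 0 | 1 | 1 | 1 | 1 |
| 428.0 or I50.9 | 1 | 0 | 1 | 0 | 1 | 0 | 0 |
| 401.9 or I10 | 0 | 1 | 0 | 1 | 0 | 1 | 1 |

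The last two rows show that ordinary heart-failure and hypertension codes are treated the same way in every table. Only the combination codes split.

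**Points for a patient whose only relevant code is 402.91 or I11.0.**

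- CHADS2 as written: heart failure 0 + hypertension 1 = 1.
- CHA2DS2-VASc as written: heart item 1 + hypertension 1 = 2.
- CHADS2 with the Table 2 heart-failure codes: 1 + 1 = 2.

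Table 5 classes a score of 1 as Intermediate and 2 to 6 as High. With no other CHADS2 risk factor, the missing point changes the class.

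**Table 2 flag.** With 401.x-405.x / I10-I16.x in place of the present list, hypertension goes from 0 to 1 for the same patient. The heart-failure flag stays at 1.

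**What removes each error.** Any record that meets the Table 2 hypertension row under the Section 9.3.3 capture rule, such as a qualifying 401.x or I10 record, corrects the first. A 428.x or I50.xx record corrects the CHADS2 item. One isolated outpatient 401.x or I10 claim would not correct Table 2, because the rule needs an inpatient claim or two visits.

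**The case against.** The strongest reply is that few patients are affected and that the model has other routes to the same information. Much of this stands.

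- **Other codes.** A reader might infer that every patient coded 402.x1 or I11.0 is misclassified. That is not so. The conflict needs the absence of any other qualifying code in the baseline year.
- **Redundancy.** The Table 2 heart-failure flag, CHA2DS2-VASc and HAS-BLED hypertension all count these patients, and antihypertensives, beta blockers and diuretics are separate covariates. The final covariate list is still to be decided, and the same lists apply to every treatment group. This limits the harm but does not make the two fields correct.
- **Different constructs.** Section 9.3.3 words the CHA2DS2-VASc item more broadly, adding left ventricle dysfunction. That could explain its cardiomyopathy codes. It does not explain why CHADS2 omits codes that Table 2 labels heart failure, or the gap in Table 2 hypertension.

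Two wider readings are tempting but not supported. Charlson (Table 4) also limits heart failure to 428.x / I50.xx, but it is a separate index that may keep its own code set. The Table 6 heart item also omits I42.0, which Table 2 includes under cardiomyopathy. That concerns a different patient and a differently named condition. Table 6 is selective on both sides: it takes only 425.4, 425.5 and 425.7 in ICD-9, and it also omits I42.1 to I42.4 and I42.7. The documents give no crosswalk to show that I42.0 was left out by mistake.

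**Conclusion.** The inconsistency is real and follows from the code lists alone. For a patient whose only qualifying codes are the combination codes, Table 2 hypertension is wrong by the definitions in Tables 5 to 7. CHADS2 is one point short by the definitions in Tables 2 and 6. The error for each such patient is certain, given the wildcard reading above.

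The number of such patients is unknown. A reader might multiply an assumed heart-failure share of 20-30% by an assumed 5-15% coded only through combination codes, giving 0.20 × 0.05 = 1.0% to 0.30 × 0.15 = 4.5%. Neither factor is in the documents. The two errors also concern different subgroups (no other hypertension code; no other heart-failure code), so one product cannot size both.

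The effect on the hazard ratios is probably small, because the lists are common to all groups and the information is largely carried elsewhere. The point is worth acting on because these fields are candidate propensity-score covariates and balance-table rows, and the correction costs little.

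**What to change.** 1. Set Table 2 Hypertension to 401.x-405.x / I10-I16.x, as in Table 7. Tables 5 and 6 also count 437.2 / I67.4 as hypertension and Table 7 does not, so state whether these belong in Table 2.
2. Add 402.x1, 404.x1 and 404.x3, with I11.0, I13.0 and I13.2, to the CHADS2 heart-failure item in Table 5.
3. Leave Charlson as it is, and do not add I42.0 to Table 6 on this evidence. At most, ask the sponsor to check the ICD-9 to ICD-10 mapping of the 425.x codes there.

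The cost is a code-list edit and minor reprogramming, with no new data and no design change. If matching has already been run, the propensity score and the balance tables would have to be rerun.

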9.3.3 Covariates

The following variables, but not limited to, will be used as covariates in the relevant analysis:

- **Gender:** Gender will be determined from eligibility file. Dichotomous variable (male=1, female=0).
- **Age:** Age in years will be determined on the index date. Continuous variable.
- **Geographic location:** Geographic locations of patient residence will be determined from eligibility file and will be grouped based on the US census classification (i.e., Northeast, Midwest, South, and West regions). South region will be the reference location.
- **Health plan type:** Health plan benefit designs such as health maintenance organization (HMO), preferred provider organization (PPO), fee-for-service (FFS), Medicare Advantage and Part D plan, etc. FFS is the reference plan type.
- **Baseline comorbid conditions:** The comorbid conditions will be captured by any inpatient claim, any two physician office visit (OV) or emergency room (ER) visits,

or a combination of both (OV+ER) with a diagnosis of the following conditions in any position during baseline (12 month pre-index period) (See [Appendix A, Table 2](#), for ICD-9-CM) and ICD-10 codes:

- Cancer
- Rheumatoid arthritis
- Coronary artery disease
- Acute myocardial infarction
- Cardiomyopathy
- Ischemic stroke
- Stroke (all types)
- TIA
- Congestive heart failure
- Left ventricular heart failure
- Hypertension
- Peripheral artery disease
- Liver disease
- Renal disease
- COPD/emphysema
- Diabetes
- Peptic ulcer (bleeding or non-bleeding)
- GERD
- Venous thromboembolism
- Hyperlipidemia
- HIV infection
- Bone marrow disease (thrombocytopenia, chronic anemia, myelofibrosis)
- Coagulopathy (hemophilia, Von Willebrand disease)
- Chronic kidney disease
- **Baseline (pre-index) medication use**
 - **Non-Oral Anticoagulants:** Number of prescription fills (normalized to a 30-day supply) will be captured during the pre-index period (See [Appendix A, Table 8](#))
 - Argatroban (can be used in procedures in lieu of heparin)
 - Unfractionated Heparin (Heparin)
 - Low Molecular Weight Heparins:
 - Enoxaparin
 - Tinzaparin
 - Dalteparin
 - Fondaparinux
 - **Other medication use:** Use of other medications will be determined if patients had ever filled a medication in the following drug classes during the pre-index period (See [Appendix A, Table 3, Table 8](#)).
 - Beta blockers
 - Calcium channel blockers
 - Diuretics

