Corticosteroids	22	2210001000, 2210001020, 2210001200, 2210001510, 2210002000, 2210002010, 2210002020, 2210002500, 2210002540, 2210003000, 2210003010, 2210003020, 2210004000, 2210004010, 2210004020, 2210004500, 2210005010, 2210005020, 2210005022, 2210005030, 2210990210, 2210990215, 2210990258, 2210990260, 2210990262, 2210990263, 2210990265, 2210990285, 2210990287, 2210990290, 2210990308, 2210990310, 2210990315, 2210990320, 2210990350, 2210990360, 2210990370, 2210990373, 2210990420, 2220003010

Antidiabetics	27	2710400200, 2710400300, 2710400400, 2710400500, 2710400600, 2710400700, 2710401000, 2710402000, 2710407000, 2710408000, 2710409000, 2715005010, 2717001000, 2717001500, 2717002000, 2717005000, 2720002000, 2720002700, 2720003000, 2720004000, 2720004010, 2720005000, 2720006000, 2725005000, 2728004000, 2728006000, 2730001010, 2730001015, 2730002000, 2730003000, 2730405000, 2730990240, 2750001000, 2750005000, 2755001010, 2755005000, 2755006510, 2755007010, 2757402010, 2760705010, 2760706010, 2770002000, 2770004020, 2770005000, 2799250210, 2799250240, 2799250260, 2799250270, 2799300270, 2799400210, 2799500270, 2799600220, 2799600230, 2799600240, 2799650230, 2799700235, 2799700240, 2799780240, 2799780260, 2799800240, 2799800260, 2799900250
Antiarrhythmics:		
Amiodarone HCl	3540000	3540000500
Propafenone and Flecainide	353000	3530005000
Dronedarone	35400028	3540002810
Betapace (Sotalol)	33100045	33100045
Tikosyn	35400025	3540002500
Disopyramide (Norpace)	35100010	3510001010
Quinidine	351000301	3510003010, 3510003030
Ketoconazole	11404040	1140404000

Table 4. Charlson Comorbidity Index Calculation

Programming algorithm for the Charlson Comorbidity Index (CCI)

1. Identify all patients who ever had the following conditions during their baseline period.

Condition		
Myocardial Infarction	410.x, 412.x	I21.xx, I22.x, I25.2
Congestive Heart Failure	428.x	I50.xx
Peripheral Vascular	441.x, 443.9x,	I71.xx, I73.9, I96, Z95.828

Disease	785.4x, V43.4x	
Cerebrovascular Disease	430.x-438.x	G45.0-G45.2, G45.4-G46.8, I60.xx-I69.xxx (exclude I67.3, I67.83)
Dementia	290.x	F01.5x, F03.90
Rheumatologic Disease	710.0x, 710.1x, 710.4x, 714.0x, 714.1x, 714.2x, 725.x, 714.81	M05.xx-M06.9 (exclude M06.4), M32.xx, M33.20, M34.xx, M35.3
Peptic Ulcer Disease	531.4x-531.7x, 532.4x-532.7x, 533.4x-533.7x, 534.4x-534.7x, 531.0x-531.3x, 532.0x-532.3x, 533.0x-533.3x, 534.0x-534.3x, 531.9x, 532.9x, 534.9x	K25.0-K28.9

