	Exclusion	EXCLUDE above codes if “traumatic brain injury” ICD-9-CM code (800 to 804, 850 to 854) or “rehabilitation care” as the primary ICD-9-CM code (V57) is present.	S02.xxxA, S02.xxxB, S06.xxxA, Z51.89
Major Intracranial Bleeding (Primary or Secondary)	430	Subarachnoid hemorrhage	I60.xx
	431	Intracerebral hemorrhage	I61.x
	432.x	Other and unspecified intracranial hemorrhage	I62.xx
	852.0	Subarachnoid hemorrhage following injury without mention of open intracranial wound	S06.36xA
	852.2	Subdural hemorrhage following injury without mention of open intracranial wound	S06.4XXA
	852.4	Extradural hemorrhage following injury without mention of open intracranial wound	S06.5XXA
	853.0	Other and unspecified intracranial hemorrhage following injury without mention of open intracranial wound	S06.6XXA

	Exclusion	EXCLUDE – above codes if concomitant discharge diagnosis of major trauma was present (ICD-9 codes 852.1, 852.3, 852.5, and 853.1)	S01.90XA, S06.36xA, S06.4XxA, S06.5XxA, S06.6XxA
Major Extracranial		Inclusive of major GI bleeding, major urogenital bleeding and major other bleeding	
Major GI Bleeding		Inclusive of major upper GI bleeding and major lower GI bleeding	
Major upper GI bleed (Primary Only)	531.0x	Acute gastric ulcer with hemorrhage with/without obstruction	K25.0
	531.2x	With hemorrhage and perforation with/without obstruction	K25.2
	531.4x	(chronic or unspecified gastric ulcer with hemorrhage with/without obstruction)	K25.4
	531.6x	(with hemorrhage and perforation with/without obstruction)	K25.6
	532.0x	(acute duodenal ulcer with hemorrhage with/without obstruction)	K26.0
	532.2x	(with hemorrhage and perforation with/without obstruction)	K26.2
	532.4x	(chronic or unspecified duodenal ulcer with hemorrhage with/without obstruction)	K26.4
	532.6x	(with hemorrhage and perforation with/without obstruction)	K26.6
	533.0x	(acute peptic ulcer of unspecified site with hemorrhage with/without obstruction)	K27.0
	533.2x	(with hemorrhage and perforation with/without obstruction)	K27.2
	533.4x	(chronic or unspecified peptic ulcer of unspecified site with hemorrhage with/without obstruction)	K27.4
	533.6x	(with hemorrhage and perforation with/without obstruction),	K27.6
	534.0x	(acute gastrojejunal ulcer with hemorrhage with/without obstruction)	K28.0
	534.2x	(with hemorrhage and perforation with/without obstruction)	K28.2
	534.4x	(chronic or unspecified gastrojejunal ulcer with hemorrhage with/without obstruction)	K28.4

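### The Table 2 peptic ulcer row holds only ulcers of unspecified site, merged with reflux and dyspepsia, so ulcer history is not measured or checked for balance as its own covariate

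*Combined protocol and SAP*

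**What the plan says.** Section 9.3.3 lists "Peptic ulcer (bleeding or non-bleeding" as one baseline comorbidity and GERD as the next. Section 9.7.1 repeats both. Section 9.3.3 points to Appendix A Table 2 for the codes.

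Table 2 has a single row, "Peptic ulcer/GERD". Its ICD-9 codes are "530.11, 530.81, 536.2, 536.8, 787.1, 533.xx" and its ICD-10 codes are "K21.x, K27.x, K30, R11.10, R12". Further down, the same table has a Dyspepsia row made up of 536.8 and K30, both of which are already in the merged row.

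Other tables in Appendix A treat ulcers more fully:

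- Table 4 (Charlson index) lists ulcers at all sites, including "531.4x-531.7x, 532.4x-532.7x, 533.4x-533.7x, 534.4x-534.7x", and K25.0 to K28.9 in ICD-10.
- Table 7 (HAS-BLED) lists hemorrhagic ulcers in all four categories, 531 to 534, within its bleeding item.
- Table 9 (outcomes) labels 533.0x as "acute peptic ulcer of unspecified site with hemorrhage with/without obstruction". It gives 531.0x its own line ("Acute gastric ulcer with hemorrhage with/without obstruction") and 532.0x another ("acute duodenal ulcer with hemorrhage with/without obstruction"). All of these count as major upper GI bleeding, and hence as major bleeding, a primary outcome.

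Section 9.7 names the Charlson index, the modified HAS-BLED score and the relevant comorbidities as candidate propensity score variables. It leaves the final list to be agreed with the sponsor. Covariates not sufficiently balanced after matching are to enter a multivariate model.

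**The concern.** The variable that Table 2 would produce is not the one Section 9.3.3 names. A patient whose only relevant code is a gastric or duodenal ulcer gets a zero on the flag. A patient with reflux or dyspepsia and no ulcer gets a one.

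Hemorrhagic ulcer codes are part of the primary major-bleeding outcome, and the sponsor itself chose ulcer history, bleeding or not, as a baseline covariate. The matched balance table would carry a row headed peptic ulcer that leaves out three of the four ulcer categories. If ulcer history differed between the matched groups, that table could not show it, and the plan's remedy for residual imbalance acts only on covariates that have been measured.

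**Working it through.** The plan gives no figure on this point to reproduce, so the check is a comparison of code lists followed by an illustrative bias calculation.

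**1. Coverage.** The reference set is ICD-9 categories 531, 532, 533 and 534 with fourth digits 0 to 7 and 9: 4 × 9 = 36 subcategories. The hemorrhagic ones, following Table 9, have fourth digits 0, 2, 4 and 6: 4 × 4 = 16.

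| List | All ulcer (of 36) | Hemorrhagic (of 16) | ICD-10 categories K25-K28 (of 4) |
|---|---|---|---|
| Table 2 merged row | 9 (533 only) | 4 | 1 (K27) |
| Table 4, Charlson | 35 (533.9 absent) | 16 | 4 |
| Table 7, HAS-BLED bleeding item | 16 | 16 | 4, hemorrhagic codes only |
| The three lists together | 36 | 16 | 4 |

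Table 2 therefore misses 36 − 9 = 27 subcategories, of which 16 − 4 = 12 are hemorrhagic. No other Table 2 row contains an ulcer code.

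**2. What the composite scores carry.** Non-bleeding gastric, duodenal and gastrojejunal ulcers reach the propensity score only through the Charlson index. That index is a weighted sum, so two patients can share a value with and without an ulcer. Hemorrhagic ulcers also reach it through HAS-BLED, but anemia, hematuria or epistaxis codes satisfy the same item. Matching on either score does not ensure that ulcer history itself is balanced, and neither shows whether it is.

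**3. Possible size.** With ulcer prevalences p1 and p0 remaining in the two matched groups and a rate ratio RR for major bleeding given ulcer history, the multiplicative bias in the treatment rate ratio is

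(1 + p1(RR − 1)) / (1 + p0(RR − 1)).

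All inputs here are assumptions.

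| p0 versus p1 | RR = 2 | RR = 3 |
|---|---|---|
| 1% versus 2% | 1.02/1.01 = 1.010 | 1.04/1.02 = 1.020 |
| 2% versus 3% | 1.03/1.02 = 1.010 | 1.06/1.04 = 1.019 |
| 1% versus 3% | 1.03/1.01 = 1.020 | 1.06/1.02 = 1.039 |
| 5% versus 7% | 1.07/1.05 = 1.019 | 1.14/1.10 = 1.036 |

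The range is about 1% to 4%. In these examples it depends mainly on the residual difference and the RR, and little on the prevalence level.

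**4. Benchmark.** Section 9.5 gives detectable differences in major bleeding, at 80% power, of 22% (rivaroxaban) and 37% (apixaban). Both reproduce. Expected events are 0.9 × 16,000 × 0.82 × 0.031 × (1 + 1.22) ≈ 813 and 0.9 × 6,000 × 0.82 × 0.031 × (1 + 1.37) ≈ 325. The Schoenfeld formula, power = Φ(√(events/4) × ln HR − 1.96), gives 0.809 and 0.810. A bias of 1% to 4% is small on that scale.

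**The case against.** The strongest reply is that ulcer history is not left out of the adjustment. The Charlson index covers 35 of the 36 ICD-9 subcategories and Table 2 supplies the last one. HAS-BLED covers every hemorrhagic code. Both scores are named propensity inputs. The Charlson list also counts anyone with the condition at any time in baseline, which is looser than the Table 2 rule of one inpatient claim or two visits. The covariate list is open-ended (Section 9.3.3), the abstract allows frequent diagnoses to be added empirically, and Section 9.5 calls the analyses exploratory.

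Most of this stands, and it rules out three stronger readings that a reader might draw from Table 2:

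- **That ulcer history is unbalanced between the drugs.** A protocol cannot show this. Partial adjustment is planned, and the same code list applies to every group.
- **That patients with gastric or duodenal ulcers are treated as ulcer-free.** This is true only of the Table 2 flag, and only if they have no other code in the row. They still score on the Charlson index.
- **That the flag mostly marks reflux.** This is plausible, but the documents give no prevalences.

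The reply does not repair the row. A summed score cannot be read as an ulcer balance check, and an open list does not ensure that a correct ulcer variable will be built.

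**Conclusion.** The inconsistency is established from the documents. Following the plan as written produces a peptic ulcer variable limited to unspecified-site ulcers and mixed with reflux and dyspepsia, contrary to the two separate covariates in Sections 9.3.3 and 9.7.1. Ulcer history is adjusted only indirectly, and the Section 9.7 provision for residual imbalance cannot be triggered for it.

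The effect on the major-bleeding rate ratio is probably small, about 1% to 4%. That range assumes a difference of 1 to 2 percentage points remaining after matching on the Charlson index and HAS-BLED, together with a 2- to 3-fold bleeding risk. Neither figure is in the documents, and the direction is unknown. Bias of this kind does not shrink with sample size, and Section 9.5 states estimation as the aim. The row should be corrected, but the point does not by itself call the primary comparison into question.

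**What to change.** In Appendix A:

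- Split the merged Table 2 row. Peptic ulcer becomes 531.xx-534.xx / K25.x-K28.x. GERD becomes 530.11 and 530.81 / K21.x.
- Have the sponsor confirm the GERD codes and decide where 536.2, 787.1, R11.10 and R12 belong, because the documents do not label these codes individually.
- Keep 536.8 / K30 only in the Dyspepsia row.
- Add 533.9x to the peptic ulcer row of Table 4.

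In Section 9.7, enter peptic ulcer and GERD as separate terms in the propensity model and report a standardized difference for each before and after matching.

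The cost is a code-list correction with no new data. Section 6 planned programming-rule development from 19 October 2016 and analysis from 5 December 2016, both before the protocol date of 15 December 2016. Covariate programming, the propensity model and the matching may therefore have to be rerun.
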